### **2.2 Secondary Objectives**

The secondary objectives of this study are to:

- 2.2.1 Determine the feasibility, acceptability, and fidelity of a TI-CBT intervention.
- 2.2.2 Evaluate whether a TI-CBT Intervention is associated with improved depression, anxiety, and/or traumatic stress symptoms for youth living with HIV compared to a Discussion Control following the last group session and at 12 months.
- 2.2.3 Assess whether a TI-CBT Intervention is associated with improved ART adherence (hair samples, self-report) and viral suppression (HIV RNA plasma) for youth living with HIV compared to a Discussion Control following the last group session and at six and 12 months.
- 2.2.4 Assess whether a TI-CBT Intervention is associated with improved structural factors for youth living with HIV (HIV stigma and support for adherence; barriers to adherence; gender-based violence; gender roles) compared to a Discussion Control following the last group session and at six and 12 months.
- 2.2.5 Assess whether a TI-CBT Intervention is associated with improved structural factors for caregivers (HIV knowledge, stigma, and support for adherence; barriers to adherence) compared to a Discussion Control following the last group session and at six and 12 months.
- 2.2.6 Assess whether a TI-CBT Intervention is associated with improved behavioral risk outcomes for youth living with HIV (alcohol/drug use; sex-risk behaviors; caregiver report of youth behavior) compared to a Discussion Control following the last group session and at six and 12 months.
- 2.2.7 Identify the individual, social, and structural barriers, and facilitators to implementation of a TI-CBT Intervention.
- 2.2.8 Compare the rates of all targeted adverse events between a TI-CBT Intervention and a Discussion Control for youth living with HIV.

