## 2.3 Other Objectives

The other objectives of this study are to:

- 2.3.1 Evaluate whether a booster session at six months is associated with continued improvements in depression, anxiety and traumatic stress symptoms at 12 months.
- 2.3.2 Assess whether youth and caregiver demographic and structural factors moderate the efficacy of a TI-CBT Intervention compared to the Discussion Control.

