Eligibility screening will be initiated after informed consent and assent (if applicable) are provided. As part of the youth informed consent/assent process, youth will be asked whether they are willing to identify a caregiver and provide written permission for the caregiver to participate in the study. Youth who cannot identify a caregiver or do not otherwise provide written permission for caregiver participation remain eligible to enroll as youth can benefit from participation in the intervention without caregivers. If the identified caregiver agrees to participate, they will be introduced to the study and asked to provide informed consent for their own participation. This can be done at any point between youth screening and the first caregiver group session.

Given that each TI-CBT and Discussion Control group should include 6-10 youth per group, sites will need to identify a pool of 12-20 eligible youth to be enrolled/randomized at one time (refer to [Section 6.3.3](#)). Enrollment/randomization must occur within 60 days of each youth participant initiating the screening process. Therefore, sites must screen a sufficient number of potential youth participants within this time period to ensure that 12-20 can be enrolled/randomized on a given

day. The first TI-CBT Intervention and Discussion Control group sessions will be conducted on the day of enrollment/randomization.

Groups will be mixed gender unless a site determines that single gender groups are more appropriate for youth participants during the ADAPT-ITT process. Sites will develop appropriate SOPs accounting for the gender composition and related recruitment process as determined appropriate from the ADAPT-ITT process.

Once a sufficient pool of eligible youth has been identified, the site will schedule the Entry Visit and first group session (the first group session will occur on the day of the Entry Visit). Prior to the Entry Visit, eligible youth will be scheduled for a Pre-Entry Visit to complete baseline evaluations. This visit can occur on the same day or within 14 days prior to the Entry Visit. Youth who are screened more than 60 days prior to enrollment must be re-screened for all inclusion and exclusion criteria prior to enrollment. The youth will not be enrolled if deemed ineligible following repeat of screening evaluations. For details on randomization, refer to [Sections 6.3.3](#) and [9.3](#).

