Caregivers identified by youth to participate in the study will be contacted by study staff and invited to visit the clinic to learn more about the study and undergo an informed consent process for their study participation. Consenting caregivers will be enrolled and complete baseline evaluations at their Entry Visits. Caregiver Entry Visits may occur prior to or on the same day as the first caregiver group session.

When informed consent or assent is obtained, a unique participant identification number (PID) will be assigned to each of the youth and caregiver participants by the site. The IMPAACT Data Management Center (DMC) Study Enrollment System (SES) will be used for both the screening and enrollment of youth participants and used only for enrollment of caregiver participants. Screening and enrollment processes will differ for youth and caregiver participants as follows:

- **Youth:** A study-specific screening number will be obtained through the SES for all youth for whom informed consent and assent (if applicable) is provided. Screening numbers will be generated by the SES upon successful entry of data into a study-specific screening checklist. For screened youth found to be eligible, enrollment will occur upon successful entry of required eligibility checklist data into the SES. Successful enrollment will generate a study identification number (SID) for youth in the Pilot Test and the Randomized Trial; the SES will also generate a random assignment — to either the TI-CBT Intervention or the Discussion Control arm — for youth enrolled in the Randomized Trial. Youth from the same household will be assigned to the same arm; the eligibility checklist will be used to determine the assignment for additional youth enrolled based on the first youth enrolled from the same household. The generation of the SID is the effective point of enrollment in the study.
- **Caregiver:** After successful enrollment of their youth, eligible caregivers will be enrolled through the same eligibility checklist that will link the PID numbers of the youth and caregiver through additional questions in the eligibility checklist. For the Randomized Trial only, the caregiver will receive the same random assignment as their youth upon the PID linkage. The generation of the SID is the effective point of enrollment in the study.

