### Caregiver Participants

**TI-CBT sessions:** Caregivers of youth in the Pilot Test and of youth randomized to the TI-CBT Intervention Arm in the Randomized Trial will receive two 2-hour group sessions on two separate weeks within eight weeks of their youth's first group session. These sessions will occur separate from the youth sessions. Refer to [Table 3](#) for specific content to be delivered in a given session.

All sessions will be delivered by adult study staff who will follow a detailed TI-CBT Caregiver Intervention Manual (refer to [Section 5.1.1.1](#)). Caregiver sessions are designed to improve caregiver's HIV knowledge, reduce caregiver stigma about HIV, educate caregivers about youth-reported obstacles to ART adherence, increase caregiver efforts to help youth adhere (e.g., attend clinic appointments, reminders to take medication), and strategies to improve caregivers' communication with youth about adherence. Role-play will be used to enact different adherence scenarios to teach caregivers how they may offer adherence support.

**Booster session:** In the Randomized Trial only, a booster group session will be conducted after completion of the six-month follow-up evaluation, on the same day or within one month, to enhance sustainability of intervention effects. This session will consist of one 2-hour condensed review of the original caregiver session material, emphasizing the importance of youth ART adherence and how caregivers can assist youth in their adherence efforts. The session will offer opportunities for open discussion and questions from the caregivers.

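### Caregivers may consent and complete baseline questionnaires after the youth's arm is known, so the caregiver comparisons (2.2.5, CBCL in 2.2.6) and caregiver structural moderators (2.3.2) are not fully protected by randomization

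*Protocol*

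**What the plan says.** **Youth.** Protocol 4.6 fixes the arm and the start of treatment on one day: "The first TI-CBT Intervention and Discussion Control group sessions will be conducted on the day of enrollment/randomization". Youth screening measures and Pre-Entry questionnaires come before the assignment (6.3.1, 6.3.2).

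**Caregivers.** The youth is asked at consent and screening whether to name a caregiver and permit participation. The caregiver's own introduction and consent have a wider window: "This can be done at any point between youth screening and the first caregiver group session". Baseline questionnaires belong to the caregiver Entry Visit, and "Caregiver Entry Visits may occur prior to or on the same day as the first caregiver group session". Section 5.1.1 places the two caregiver sessions "on two separate weeks within eight weeks of their youth's first group session", and 5.1.2 does the same for the control arm. The schema shows them in Weeks 1 to 6. Footnote 1 of Appendix II-B lets caregiver screening and entry procedures run alongside the youth's Screening, Entry or group-session visits.

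**Allocation.** Formal caregiver enrollment follows the youth's: "After successful enrollment of their youth, eligible caregivers will be enrolled through the same eligibility checklist", and "the caregiver will receive the same random assignment as their youth upon the PID linkage".

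**Use of the data.** Objective 2.2.5 reads "Assess whether a TI-CBT Intervention is associated with improved structural factors for caregivers", compared with the Discussion Control. Objective 2.2.6 includes the caregiver-reported CBCL. Objective 2.3.2 reads "Assess whether youth and caregiver demographic and structural factors moderate the efficacy of a TI-CBT Intervention". Protocol 9.5.2 says only that other outcomes get analyses similar to the primary one. SAP 1.1 leaves the detail to a separate SAP for Other Outcome Measures, which is not among the documents.

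**The concern.** Caregivers are not randomized themselves; they inherit the youth's arm. Neither document describes masking that arm from the caregiver or from the staff who invite caregivers. A caregiver can therefore decide whether to join after the arm is known and after the youth has attended sessions. What is on offer differs by arm: a manualized HIV and adherence curriculum, or topics that the caregivers choose. If the caregivers who join differ between arms, a difference in stigma, knowledge or CBCL can come from who joined.

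The analysis sets do not cover this. Protocol 9.5 includes all randomized participants and SAP 4.1.1 defines intention-to-treat on randomized youth. A caregiver who was invited but never enrolled contributes no data to any set.

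The second problem concerns moderation. A caregiver attitude recorded after the youth's sessions began may already reflect them. Later analysis cannot recover the earlier value.

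The protocol guards against a related risk for youth: section 9.1 ties randomization to the first session day to limit differential drop-out. Caregivers have no equivalent safeguard.

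**Working it through.** The documents state no caregiver sample size, power or uptake rate, so there is no planned figure to reproduce. The check covers timing, then what each analysis uses, then an illustration with assumed inputs.

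**1. Latest caregiver baseline.**
- Eight weeks from youth Session 1 is 8 × 7 = Day 56.
- Sessions A and B fall in separate weeks. If B is on Day 56, A is about Day 49 (a week earlier) and at most Day 55, or about week 7.
- Under the schema's Weeks 1 to 6, A falls by about week 5.
- Six youth sessions in Weeks 1 to 6 is about one a week. A baseline in week 5 could follow four or five of them, and one in week 7 could follow all six.
- The earliest option is the youth's Screening visit, before randomization. The plan permits the whole range.

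**2. What each analysis uses.**

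| Analysis | Late enrollment | Late baseline |
|---|---|---|
| 2.2.5, and CBCL in 2.2.6: follow-up group means by arm | Affected | Not used in the stated comparison |
| 2.3.2, caregiver structural factors | Affected | Affected |
| 2.3.2, caregiver demographics | Known only for enrolled caregivers | Little changed by timing |
| 2.3.2, youth factors | Not affected | Not affected |
| Primary youth comparison | Not affected | Not affected |

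**3. How large selection could be (all inputs assumed).** Let willingness to join be a latent normal variable with correlation ρ to the outcome, and let uptake be p1 and p0 in the two arms. With z the standard normal quantile cutting off the joining fraction p, the spurious difference is

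bias = ρ × [φ(z0)/p0 − φ(z1)/p1] in SD units.

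The values of φ(z)/p are 0.195 at 90%, 0.350 at 80%, 0.497 at 70% and 0.644 at 60%.

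- 80% v 70%: 0.147ρ, or 0.03 SD at ρ = 0.2 and 0.07 SD at ρ = 0.5.
- 80% v 60%: 0.294ρ, or 0.06 to 0.15 SD.
- 90% v 60%: 0.449ρ, or 0.09 to 0.22 SD.
- 70% in both arms with the same ρ: zero.
- 70% in both arms, ρ = 0.3 in one and 0 in the other: 0.3 × 0.497 = 0.15 SD. Equal uptake alone is therefore not proof of no bias.

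For the effect on false positives, take m groups per arm of n = 8 youth, so n·p caregivers per group, and assume the youth ICC range applies to caregivers:

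SE² = [1 + (n·p1 − 1)ICC]/(m·n·p1) + [1 + (n·p0 − 1)ICC]/(m·n·p0), with a two-sample t-test on 2(m − 1) df.

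Across m = 12 or 16 at ICC 0.05 and m = 12 at ICC 0.15, and ρ from 0.2 to 0.5, the nominal 5% error becomes about 5 to 7% (80% v 70%), 6 to 14% (80% v 60%) and 7 to 26% (90% v 60%).

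**The case against.** The strongest reply has five parts.

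- **Permitted, not required.** Caregiver procedures may take place at youth Screening, and youth permission is sought before randomization. This stands. The youth who gave permission at screening form a denominator that randomization protects. (Section 6.4.1 lists youth agreement again at caregiver entry, possibly only to confirm it, so the screening-stage record is the one to use.) A reader might infer that caregiver results have no protection at all; the text does not support that.
- **No change score is planned.** This also stands. Protocol 9.5.1 and 9.5.2 compare follow-up group means. A reader might infer that a late baseline understates caregiver change, but that is not an analysis the documents set out. The CBCL recall period is six months, so even at week 7 only about 7 of 26 weeks follow Day 0.
- **The arms are matched** on number and timing of sessions, transport, compensation and refreshments. This makes unequal uptake less likely, but content still differs and the arm is not masked.
- **Uptake will be visible.** SAP 5.2.1 and 5.2.2 report caregivers approved and enrolled, and caregiver baseline characteristics, by arm. Protocol Table 4 lists the proportions of youth inviting a caregiver and of invited caregivers agreeing, but as per-site measures. These are descriptive, and no analysis follows from them.
- **Low tier, plan not seen.** Caregiver measures are other outcomes, and their SAP may address selection. It cannot supply a pre-randomization value that was never collected.

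**Conclusion.** The timing is certain from the text: a caregiver may consent and give baseline answers after the arm is known and youth sessions have begun. The consequence is limited. The 2.2.5 comparison and the caregiver-reported CBCL in 2.2.6 are not fully protected from selective enrollment by arm. Caregiver stigma, knowledge, support and barriers measured after Day 0 are not clean moderators for 2.3.2.

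The size is unknown. The 0.03 to 0.22 SD illustrated for unequal uptake rests wholly on assumed uptake gaps and correlations. It shows what selection could do and does not estimate what it will do.

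A reader might also infer that all of 2.3.2 fails, or that the youth result is compromised. Neither follows. Youth moderators are recorded at Screening and Pre-Entry, caregiver demographics such as education are not a timing problem, and the primary group-level comparison uses no caregiver data.

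The change is worth making because it turns an option the protocol already allows into the preferred one.

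**What to change.** **Protocol 4.6, 6.4.1 and Appendix II-B.** Ask for caregiver consent and the baseline questionnaires before the youth's assignment in the enrollment system where possible: at youth Screening, at Pre-Entry, or on Day 0 before assignment. Formal caregiver enrollment can stay after the youth's, but the wording of 4.6 that ties the questionnaires to enrollment at the Entry Visit needs adjusting. Caregivers identified later may still join and attend.

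**SAP for Other Outcome Measures.**
1. Flag each caregiver's consent and baseline dates relative to Day 0.
2. Compare caregiver uptake by arm among youth who gave permission at screening.
3. Restrict caregiver structural moderators in 2.3.2 to values recorded before randomization.
4. Repeat the 2.2.5 and CBCL comparisons in caregivers who consented before randomization, as a sensitivity analysis. Define the set by consent date, and count those who consented but did not go on to enroll as missing.

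The early-consenting set should not replace the main comparison. It depends on site scheduling and could be small. If enrollment is already complete, the SAP items can still be done from dates on record.

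**Cost.** More scheduling before Day 0, and less precision in the moderator analysis. Some caregivers would complete baseline for youth who are never randomized: at the 15% attrition that Protocol 9.3.1 expects between screening and first session, about 3 of every 20 youth who pass screening (0.15 × 20).

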#### **4.7 Participant Retention (Pilot Test/Randomized Trial)**

Once a youth and/or caregiver participant is enrolled in the study, study staff will make every effort to retain him or her for the protocol-specified duration of follow-up, thereby maximizing statistical power and minimizing potential biases associated with loss to follow-up. Each site must establish and implement SOPs that target retention rates that are sufficient to reliably estimate the primary study outcomes (10% loss to follow-up between evaluations is assumed in sample size calculations). Refer to [Section 9.4](#) for more information on monitoring participant retention in this study.

Site SOPs should include measures taken to maintain current phone/text/email, and/or in-person contacts of participants and approximately three close contacts at each study visit to enable scheduling and remind participants of each evaluation and group session. Youth (and caregivers where relevant) will be contacted by study staff prior to each group session and evaluation to confirm attendance. Refer to the study-specific MOP for additional guidance on tracking procedures used in past studies to reduce attrition and sample size bias.

#### **4.8 Participant Withdrawal or Termination from the Study (Pilot Test/Randomized Trial)**

##### Temporary Hold from the Study

Disruptive youth will be removed from the current group session (TI-CBT or Discussion Control group session) at the discretion of the designated on-site study clinician as described in [Section 8.1](#). The youth will be allowed to return to the following group session. The youth will be advised that the behavior is unacceptable and if the behavior is not resolved and continues, they will be removed from the study as indicated below.

##### Permanent Withdrawal or Termination from the Study

Youth participant/legal guardian and caregiver participants may voluntarily withdraw from the study. Participants may also be permanently terminated from the study by the site investigator or designee under the following circumstances:

- Participant re-locates away from the study site and is unreachable or is otherwise determined to be lost-to-follow-up, with no options for transfer to another site.
- The study is stopped or canceled by the sponsors, government or regulatory authorities, or site IRBs/ECs
- The participant fails to comply with study requirements and/or is disruptive, so as to cause harm to self or others, seriously interfere with the validity of the study results, or otherwise would not be in the best interest of the participants and study staff, after Investigator or designee consults with the CMC.

For any participant who withdraws or is terminated from the study prior to scheduled completion of follow-up, study staff will document the reason for the withdrawal or termination in detail. If the circumstances that led to a participant's withdrawal or termination change (e.g., he or she returns to the study site area after having re-located previously), the site investigator or designee will contact the CMC to discuss options for resumption of follow-up.

Youth participant withdrawal or termination does not impact their respective caregiver participation and vice versa.

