## **6 STUDY VISITS AND PROCEDURES (Pilot Test/Randomized Trial)**

Refer to [Section 4.6](#) for a description of the study recruitment, screening, and enrollment process. An overview of the study visits and evaluation schedules for youth are provided in [Appendix I-A](#) and [Appendix II-A](#). An overview of the study visits and evaluation schedules for caregivers are provided in

[Appendix I-B](#) and

[Appendix I-B](#) and [Appendix II-B](#). Presented in this section is additional information on visit-specific study procedures.

All study visits should be conducted as close as possible to the specified target visit dates and within the specified targeted windows. Every effort should be made to conduct the visits within the targeted windows; however, the visits are permitted to be conducted within the allowable windows.

Study visits and procedures will generally be performed at the clinical research site. However, if allowed per local law and regulations and/or institutional policies, participants may have study visits conducted in their home or in other off-site locations. At sites where off-site visits are permitted, study staff will discuss this option with participants in advance and agree on where and when such visits may take place, with adequate protections for participant privacy and confidentiality. Prior to each off-site visit, study staff will confirm the date, location, and time of each visit with the participant. At off-site visits when specimen collection is required, the procedures specified in [Section 6.8](#) must be followed. Off-site visits may only be conducted by designated study staff who are qualified to perform all protocol-specified procedures and have undergone study-specific and all other applicable training relevant to the procedures they will perform off site. These staff should also be adequately trained and qualified to immediately manage any adverse events and/or social harms that may occur during off-site visits (e.g., fainting during blood drawing).

All visits and procedures must be documented in accordance with the DAIDS requirements for source documentation; refer to [Section 10](#) for more information on documentation requirements and entry of eCRFs. Refer to [Section 7](#) for information on expedited adverse event (EAE) reporting, which may be required at any time during follow-up.

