### 6.3.4 Youth Randomized: Group Sessions 1-6 Study Visits

Group Session 1 for the TI-CBT and Discussion Control arms are targeted to occur on the day when group members complete their study Entry Visits and are randomized to either the TI-CBT Intervention Arm or the Discussion Control Arm. Every effort will be made to keep the TI-CBT and Discussion Control groups separated once youth are randomized to an arm (e.g., group sessions occur in separate buildings, group sessions' start times staggered so one group leaves before the other finishes, etc.)

All six group sessions within an arm should be completed within eight weeks of the date of Group Session 1. Group sessions may be conducted on separate days or multiple sessions may be conducted on the same day.

Youth Group Sessions 1-6 Procedures for Randomized Trial (within 8 weeks of Group Session 1)	
Behavioral and Counseling	
 
IYL-delivered youth TI-CBT or Discussion Control group session [refer to Section 5.1]
 
Administer after each group session: Two questions on “Amount of fun had” and “Amount learned” [refer to Section 5.5.4]
 

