### 6.3.6 Youth Randomized Trial: 6 Month Follow-up Study Visit

The 6 Month Follow-up Study Visit is targeted to take place on Day 182, counted from the day of the first group session as Day 0, with a targeted window of  $\pm 14$  days and an allowable window of  $\pm 30$  days.

Youth 6 Month Follow-up Study Visit Procedures for Randomized Trial ( $\pm 30$ days)		
Clinical		
 
Obtain targeted medical/medications history per Section 6.5
 

Behavioral and Counseling		
 
Administer electronic questionnaires - pen and paper may be substituted per Section 10.1:               
 
PHQ-9
 
GAD-7
 
UCLA PTSD exposure screener and reaction index
 
Self-report ART Adherence
 
Barriers to adherence
 
Gender-based Violence (WHO – Victim/Perpetrator)
 
Gender Roles (Rachel Jewkes)
 
AIDS-Related Stigma Scale
 
AIDS Risk Behavior Assessment (Sexual behavior/Drug and alcohol use)
 
Children’s Report of Parenting Behavior Inventory
 
Risk for Contamination
 
 
 

Laboratory	Blood	
 
Collect blood for:               
 
HIV-1 RNA (viral load test)
 
Plasma for Inflammatory biomarkers
 
 
 
Hair sample (50-60 strands) for ART concentration – to be collected from the head (scalp) only; not required if participant is bald
 

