### 6.3.7 Youth Randomized Trial: 6 Month Booster Group Session Study Visit

The 6 Month Booster Group Session should take place after completion of the 6 Month Follow-up Study Visit evaluations. For each participant in a group, the booster group session is targeted to take place on the same day (Day 182) as the 6 Month Follow-up Visit with a targeted window of up to 14 days and an allowable window of up to 30 days following the 6 Month Follow-up Study Visit.

Youth 6 Month Booster Group Session Procedures for Randomized Trial (up to 30 days following the 6 Month Follow-up Study Visit)	
Behavioral and Counseling	
 
Booster Group Session: IYL-delivered youth TI-CBT or Discussion Control 6-month Booster Group Session
 
Administer after the Booster Group Session: Two questions on “Amount of fun had” and “Amount learned” [refer to Section 5.5.4]
 

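### Section 4.8 lets continued disruption or serious non-compliance end a youth's study participation, with no stated option to stop group sessions and keep the evaluations

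*Protocol*

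**What the plan says.** Protocol Section 4.8 has two steps. Under the temporary hold, a disruptive youth leaves the current session and may return to the next. The youth is also warned that "if the behavior is not resolved and continues, they will be removed from the study as indicated below". Under permanent withdrawal or termination, the site investigator may terminate a participant from the study on several grounds. The third begins "The participant fails to comply with study requirements and/or is disruptive, so as to cause harm to self or others" and extends to serious interference with the validity of the results and to the best interest of participants and staff. It requires prior CMC consultation. If circumstances later change, "the site investigator or designee will contact the CMC to discuss options for resumption of follow-up".

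Stopping the intervention alone is written down only in Protocol Section 8, as one way to manage a psychiatric adverse event.

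Other parts of the plan aim to keep participants under observation. Section 4.7 says "study staff will make every effort to retain him or her for the protocol-specified duration of follow-up". Section 9.5 specifies an intent-to-treat analysis whatever the number of sessions attended. SAP Section 4.2.1, however, analyses only youth who have data for the measure in question.

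**The concern.** The ground for removal is mainly behaviour in the group, but the sanction also ends the evaluations, which do not need the group. A youth removed during sessions 1-6 has no 6-month score unless follow-up is later resumed, and so drops out of the complete-case primary analysis. The imputation in SAP Section 4.2.3 is confined to unscorable UCLA PTSD-RI assessments. The loss-to-follow-up analyses there compare characteristics, reasons and timing, but restore no score.

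Removal depends on behaviour after randomization, in sessions that differ by arm, among youth enrolled because of mental health distress. The loss could therefore be related to the outcome. Its direction, and whether it would differ between arms, are unknown. The rule works against both the retention aim of Section 4.7 and the intent-to-treat principle of Section 9.5.

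**Working it through.** **1. Do the evaluations depend on the group?**

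- Protocol Section 6.3.4: "All six group sessions within an arm should be completed within eight weeks of the date of Group Session 1". Eight weeks x 7 = Day 56.
- Protocol Section 6.3.6: "The 6 Month Follow-up Study Visit is targeted to take place on Day 182", with an allowable window of ±30 days. The window opens on 182 − 30 = Day 152.
- Planned time without group contact before that window: 152 − 56 = 96 days.
- Protocol Section 6.3.7: "The 6 Month Booster Group Session should take place after completion of the 6 Month Follow-up Study Visit evaluations". The booster therefore does not bring the youth back into a group before the primary outcome is measured.
- Protocol Section 6: where local rules allow, "participants may have study visits conducted in their home or in other off-site locations".

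A youth who has left the group can be assessed alone. Removal at the booster would cost only the 12-month data, because the 6-month evaluation comes first.

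**2. Does any other text supply the missing option?**

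| Protocol section | What it offers | Sessions-only withdrawal with evaluations kept? |
|---|---|---|
| 4.8, temporary hold | Out of one session, then removal from the study | No |
| 4.8, third ground | Termination from the study after CMC consultation | No |
| 8 | Stopping the intervention for psychiatric adverse events | Different trigger; silent on evaluations |
| 8.1 | Clinician intervenes, for example by removal for the rest of the session | Not stated |
| 7.1.2 | General CMC guidance, including on giving the intervention | Possible case by case; not stated |

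**3. The plan's own power figures.** Inputs are from Protocol Section 9.3.1: two-sided alpha 0.05, 80% power, m = 12 or 16 groups per arm, n = 8 per group, ICC 0.05-0.15. With

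SE = sqrt(2 × (ICC + (1 − ICC)/n) / m)

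and a two-sample noncentral t on group means with 2(m − 1) degrees of freedom, the detectable differences at ICC 0.05/0.10/0.15 are 0.49/0.55/0.61 SD (m = 12) and 0.42/0.47/0.52 SD (m = 16). These match the n = 8 rows of Table 5.

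**4. The SAP's analysis.** SAP Section 4.2.1 uses a paired t-test on group means, with pairs defined by site and wave, so df = m − 1. No extra within-pair correlation is assumed. Example, m = 12 and ICC 0.05: SE = sqrt(2 × (0.05 + 0.95/8)/12) = 0.168, and the effect with 80% power is 0.516 SD.

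| m | ICC 0.05 | ICC 0.10 | ICC 0.15 |
|---|---|---|---|
| 12 | 0.516 SD | 0.579 SD | 0.636 SD |
| 16 | 0.435 SD | 0.489 SD | 0.537 SD |

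**5. Power lost through termination.** Hold each effect fixed and replace n = 8 by 8 × (1 − loss) in both arms. The rate is an assumption, since no document gives one: 1% of 96 is 0.96 and 5% of 128 is 6.4, so about 1-6 youth per arm, none of whom returns.

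| Loss in each arm | ICC 0.05 | ICC 0.10 | ICC 0.15 |
|---|---|---|---|
| 1% | 0.28 points | 0.21 | 0.16 |
| 2% | 0.56 | 0.42 | 0.33 |
| 5% | 1.44 | 1.08 | 0.85 |

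The values for m = 12 and m = 16 agree to within 0.01 point, and the two-sample version gives the same losses to within about 0.01 point. All of these losses sit inside the 10% loss between evaluations that Sections 4.7 and 9.3.1 already assume.

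**The case against.** The strongest reply is that the real default is a case review. The temporary-hold text points to the termination text, where the wording is permissive, the conduct must be serious, the CMC must be consulted and follow-up can resume. If leaving the group solves the problem, the threshold for leaving the study may not be met. Section 8.1 gives clinicians an open-ended role, and Section 7.1.2 already lets the CMC advise sessions-only withdrawal. The plan also watches for loss: Protocol Section 9.4.2 and SAP Section 2.5 check whether missing 6-month assessments exceed 10%, and SAP Section 4.2.3 explores loss above 10% or larger loss in one arm. The numbers are small and the assumed rate has no source.

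Much of this stands. Termination is not automatic, few youth are likely to be affected, and the power cost is minor. Missing sessions does not itself end participation (Section 5), and youth who express suicidal ideation may stay on study (Section 6.7). But none of these passages states the alternative, and the temporary-hold text says removal from the study will follow. Case-by-case advice leaves that written default in place. The loss checks describe missingness or prompt a sample size review; they do not recover a score.

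A further objection is that a sessions-only default could keep in evaluations a youth whose conduct threatens validity. The existing criteria and CMC consultation remain, so such a case would still be reviewed. The consent rules in Section 12.3 are separate and unaffected. It is also true that nothing is gained when the evaluations themselves are what the youth refuses.

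**Conclusion.** The concern holds. Section 4.8 gives no stated way to stop group sessions and keep the evaluations, so following it loses an avoidable 6-month score by default, though not in every case. Under an assumed termination rate of 1-5% per arm with no return, the power cost is 0.2-0.3 points at 1% and 0.9-1.4 points at 5%. That is an upper limit on what the change can recover at those rates, because youth who refuse evaluations stay lost. The size and direction of any bias cannot be computed from the documents. The change should be made because it is simple and serves the plan's own retention and intent-to-treat aims, not because a large effect is expected. Confidence is medium.

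**What to change.** Amend the last sentence of the temporary-hold text and the third termination ground in Protocol Section 4.8. For Randomized Trial youth, state that:

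- the default is withdrawal from group sessions only, including the booster;
- the post-last-session (IPL), 6-month and 12-month evaluations continue individually, on-site or off-site under Section 6, with the IPL visit timed from the group's Session 6;
- the exceptions are withdrawn consent or assent, a youth who cannot be reached, closure of the study, or an individual evaluation that cannot be done safely.

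Keep the temporary hold, the existing criteria and the CMC consultation. Leave the text unchanged for Pilot Test youth, who have no follow-up evaluations, and for caregivers. Reporting needs no change: SAP Sections 5.1, 5.2.3 and 5.2.4 already separate non-receipt of the intervention, off-study reasons and 6-month data.

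The cost is two sentences, but through an amendment that needs IRB/EC approval and DAIDS registration (Protocol Section 13.2) at about eight sites in four countries (SAP Section 2.4). It can be bundled with the next amendment. Staff would have to arrange individual visits for a few youth who are difficult to manage. Until the amendment is in force, the CMC can advise sessions-only withdrawal case by case under Section 7.1.2.
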